8.2. Biological Samples

Samples collected under this protocol will be used to conduct protocol-related safety and immunogenicity evaluations (HTNV and PUUV assays). All specimens for laboratory testing will be collected at the University of Maryland Center for Vaccine Development. The amount of

blood to be drawn, by visit, is provided in [Appendix D](#). All samples will be collected using standard techniques and safety precautions.

General HLA testing will be performed on buccal swab samples on Day 0. This is exploratory in nature for the purpose of understanding genetics and immune responses. Future use research studies may include results of HLA testing to explore the impact of host genetics on immune responses to HTNV and PUUV DNA vaccine. Results of HLA testing will be part of research records and will not become part of a subject's medical record and will not be shared with their doctor.

If necessary, biological samples will be stored temporarily at the University of Maryland Center for Vaccine Development to await transport to appropriate laboratories for processing and analysis. Transport and storage of these biological samples will be handled according to applicable SOPs/SSPs. Upon receipt of humoral immunogenicity samples at USAMRIID, any non-used/residual sera remaining after completion of the immunogenicity testing may be retained and used for future research.

Any study for the future use of these biological samples will have the appropriate human subjects protection regulatory review and approval. In addition, a subject may decide at any point to withdraw consent for the future use of his/her samples. Should a subject withdraw consent for the use of his or her samples, any unused samples will be destroyed. Samples will be stored indefinitely after transport to USAMRIID.

8.3. Concomitant Medications

Concomitant medications will include all current medications and medications taken within 30 days prior to signing the ICF through approximately 28 days after the last study vaccination or early termination (if prior to 28 days after the last study vaccination), whichever occurs first. Medications will include prescription and over-the-counter drugs as well as herbals, vitamins, and supplements. Even though the medications of greatest concern are those taken 30 days prior to signing the ICF to 28 days post last vaccination, concomitant medications will be collected and recorded at each study visit.

Medications and non-study vaccines reported in the electronic case report form (eCRF) are limited to those received within 30 days prior to the first study vaccination through approximately 28 days after the last study vaccination.

Medications that might interfere with the evaluation of the investigational product(s) should not be used from time of study vaccination through 28 days post the last vaccination unless clinically indicated as part of the subject's health care. Medications in this category include the prohibited medications per the Subject Exclusion Criteria (see Section [7.4](#)).

The only restrictions on the use of concomitant medications by subjects during this study are medications that alter the immune system. The following medications are disallowed during the study:

- Chronic (defined as more than 14 days) immunosuppressants or other immune-modifying drugs within 6 months of study entry. For corticosteroids, this will mean prednisone, or equivalent, greater than or equal to 5 mg/day. In contrast, intranasal,

inhaled (< 800 beclomethasone mcg/day), and topical steroids are allowed during the study.

- Antibiotics for an acute illness within 24 hours or any antiviral medication taken within 72 hours of each study vaccination.
- Allergy treatment with antigen injections within 30 days prior to initial study vaccine administration and during the study.

8.4. Subject Compliance and Memory Aid Completion

Subjects who are unable to follow the study requirements and arrive at study visits will be withdrawn from the study at the PI's discretion. Poor compliance with study visits would include the inability to come to a scheduled study visit within window on 2 or more occasions.

Withdrawal procedures for such instances are detailed in Section [7.5](#).

Following each injection, subjects will be provided a memory aid (ie, fillable diary card) and instructed in its use. On a daily basis during the 14-day period after each injection subjects will evaluate and record any local or general symptoms (eg, fever, myalgia, and malaise) they experience (see Section [10.3.2](#)). To more accurately account for possible fevers, subjects will be given an oral thermometer, instructed on its use, and asked to take and record their temperature daily for the first 14 days after each injection. Also, subjects will be asked to record local reactions at the injection site (such as erythema, edema, bruising, and pain) for 14 days after each injection. To more accurately account for the size of any such reactions, subjects will be given a ruler and instructed on how to use it. Memory aids will be reviewed by an investigator at follow-up visits during the 14-day post-injection period. Memory aids will be collected from the subjects at the 14-day post-injection visit. If memory aids are not completed or returned, an investigator will review the AEs that occurred during that time frame to the best of the subject's recollection. Subjects will be instructed on the use of the memory aid and encouraged to fill it out as directed; if it is not completed or not brought to a study visit by 28 days following each dose, then a protocol deviation will be documented. The maximum intensity reported by the subject whether recorded on the memory aid or verbally reported to the study staff will be recorded in the eCRF as an AE with a grade and relationship as determined by the assessing investigator.

9. IMMUNOGENICITY ASSESSMENTS

9.1. Immunogenicity Endpoints

The endpoint used to measure immunogenicity of the HTNV DNA and PUUV DNA vaccine components is the production of neutralizing antibody titers to HTNV and PUUV. The primary assay used to detect and quantify hantavirus neutralizing antibodies will be the PsVNA50. This assay will be used on samples collected during Screen 2 to measure any prior humoral immunogenicity, and throughout the rest of the study to assess immunogenicity in response to the vaccinations, which is the secondary endpoint of the study. A PsVNA50 titer $\geq 1:20$ in 2 independent assays is considered positive. Initial immunogenicity results will be analyzed on the basis of intention-to-treat, in which the outcomes of all subjects who had at least one dose of vaccine, and contributed both pre- and at least one post-study vaccination venous blood sample for immunogenicity testing for which valid results were reported, will be analyzed with the group to which they were originally assigned, regardless of whether they completed the study. Subsequently, all subjects who completed the study and have serologic data will be included in the analysis of immunogenicity.

9.2. Sample Analysis

Blood will be collected, processed, aliquoted into samples, and shipped from the UMB CVD to USAMRIID per the laboratory manual instruction entitled “Specimen Collection, Handling/Processing and Transport for Research Blood Samples.” Samples will be stored at USAMRIID’s Nonclinical Development Division (NCDD). USAMRIID Molecular Virology Branch personnel will receive frozen sera. Samples will be thawed on wet ice and heat inactivated at 56°C ($\pm 1^{\circ}\text{C}$) for 30 ± 1 minutes in a water bath. Samples will then be stored at 4°C ($\pm 2^{\circ}\text{C}$) until assays are performed (< 5 weeks). Afterward, samples will be returned to -70°C ($\pm 10^{\circ}\text{C}$) storage. Dates of serum thawing, heat inactivation, and re-freezing will be recorded. As a control for bias, beginning at the Day 0 sampling the labels on the sera will not identify the subject or the dose/regimen the subject received. All sera will be pre-screened at a 1:20 dilution in both the HTNV and PUUV PsVNA. Positive samples will be further analyzed by PsVNA to determine endpoint titers. Depending on resources and time availability, certain samples may be directly titrated for endpoint (ie, no pre-screen); this will be recorded and documented. For those samples, a second assay will be performed to confirm the results. If PsVNA50 titers are determined in 2 independent assays, then GMTs for the combined results will be calculated.

USAMRIID SOP AP-05-16, Pseudovirion Neutralization Assay, will be used for all PsVNA. If a pre-screened sera sample has a titer of ≥ 20 , but if during re-titering for endpoint determination the sample is found to have a titer < 20 , then the more conservative < 20 value will be used. If an assay fails to meet the SOP acceptance criteria or if there is assignable cause, then the assay will be repeated. For individual specimens, if questions of accuracy arise, then those specimens will be retested. Questions of accuracy include differences in duplicates greater than 4-fold in titer, or titers $> 50,000$. If a sample is retested and the assay passes acceptance criteria, then the new value will be reported but noted as a repeat.

Data will be reported as HTNV and PUUV PsVNA50 titers. Seroconversion rate, GMT, and peak titer, for the cohorts will be determined. A contributing scientist report summarizing the

neutralizing antibody titers for the samples will be prepared after the titers for the final blood draw have been determined. Laboratory personnel can receive the list of subject treatment assignments following database lock.

In this study, up to 10 mL of blood on Days 0, 28, 56 and 140 and approximately 50 mL of blood on Day 84 will be collected for future use purposes. Any blood remaining after immunogenicity studies are conducted will be retained for future hantavirus-related research for subjects who agreed to future use of these samples. These samples will be stored at USAMRIID. The future research purposes for which this blood will be utilized are yet to be determined, but are likely to be additional immunogenicity assays; exact assays are yet to be determined.

9.2.1. Primary Immunogenicity Endpoint

The primary immunogenicity endpoint is the production of hantavirus neutralizing antibodies after vaccination as measured by PsVNA50. This information will allow calculation of seroconversion rates. Seropositivity is defined as a post-vaccination PsVNA50 titer ≥ 20 . The primary analysis variable will be the proportion of seropositive subjects (defined as PsVNA50 $\geq 1:20$) at each scheduled time point (eg, Days 0, 28, 56, 84 and 140), and the final overall rate of seroconversion over these time points. Seroconversion is defined as a post-vaccination HTNV- or PUUV-specific titer of $\geq 1:40$, or a minimum four-fold rise compared to baseline titer, and all study volunteers will begin the study with a baseline titer < 20 (eg, are seronegative). The PsVNA that will be used in this trial is a well-characterized, investigational assay that has been used in multiple research studies. This assay is based on vesicular stomatitis virus (VSV) that expresses a luciferase reporter protein. The VSV-luciferase particles are pseudotyped with hantavirus envelope glycoproteins. When the PsV successfully attach to and then enter cells, the luciferase reporter protein is expressed. If sera contain antibodies that prevent the PsV from attaching to and/or entering cells, then the reporter activity is neutralized. The reciprocal of the dilution that results in a 50% decrease is the PsVNA50 titer. The assay will be performed under GLP conditions in accordance with an SOP and will be monitored for quality by USAMRIID's quality assurance unit.

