8. TREATMENT OF SUBJECTS

8.1. Detailed Description of Study Visits

8.1.1. Screen 1/Briefing Visit (First Visit; Day -90 to Day -7)

Screening and enrollment procedures will be the same for all potential subjects. Potential subjects will undergo screening no more than 90 days prior to their planned initial injection (Day 0, Visit 1). All subject screen visit procedures will be performed on the first screening visit (Screen 1) to include clinical safety lab tests. The immunogenicity tests (HTNV and PUUV PsVNA) will be performed at a secondary screening visit (Screen 2) allowing sufficient time to process the sera while assuring subjects' safety lab values are still within accepted values within 56 days prior to first dose administration. A period of 56 days to complete screens 1 and 2 prior to enrollment is requested to accomplish not only the lengthy process of screening more than 200 people for the goal of enrolling 82 subjects, but to ensure the data from the immunogenicity tests will be returned for selection of subjects. A turnaround time of up to 4 weeks is required for results of the PsVNA immunogenicity tests (see Section 9.3). If more than 56 days has passed from the time of clinical safety lab test performance to the first vaccine dose, clinical safety lab tests will be rechecked on subjects who have passed the immunogenicity screen.

The following procedures will be performed during the initial screening/briefing visit (Screen 1):

- Brief potential subject and review of informed consent with subject
 - Obtain written informed consent for participation in the study and for HIV testing
 - Assess of subjects informed consent/protocol comprehension by administering a quiz
 - Provide copy of signed informed consent documents to subject
- Review inclusion and exclusion criteria to assess if subject is eligible for study
- Query subject for demographic information and medical history including concomitant medications
- Do a full physical examination to include the following organs and organ systems: general appearance, skin, head and neck, lungs, heart, liver, spleen, extremities, musculoskeletal, lymph nodes and nervous system. The exam will be performed by a study clinician licensed to make medical diagnoses and listed on the Form FDA 1572 as the site principal investigator or sub-investigator

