8.1.2. Screen 2 Visit (Second Visit; Day -90 to Day -7)

Screen 2 is required to determine if a potential subject, who had acceptable clinical laboratory screening results and met other eligibility criteria, has evidence of prior exposure to hantaviruses. Those who are seropositive, as defined by a Hantavirus PsVNA50 titer ≥ 20 , will not be eligible to participate in the study. A turnaround time of up to 4 weeks is required for PsVNA50 results. (see Section 9). The following procedures will be performed during the second screening visit (Screen 2):

- Collect approximately 10 mL whole venous blood for the determination of:
 - Hantavirus PsVNA50 screen for prior humoral immunogenicity

If Screen 2 falls outside of the 56-day screening window prior to first vaccination, then the following tests will also be conducted:

- Check inclusion and exclusion criteria to ensure that subject is still eligible for the study
- Query subject about interim medical history including concomitant medication use
- Do a directed physical examination if indicated based on the subject's interim medical history. The exam will be done by a study clinician licensed to make medical diagnoses and listed on the Form FDA 1572 as the site principal investigator or sub-investigator
- Take resting vital sign measurement including oral temperature, heart rate, respiratory rate, and systolic and diastolic blood pressure
- Weigh and record subject's weight. If there is a $> 15\%$ change in body weight, remeasure skinfold thickness of potential injection sites with caliper
- Collect approximately 24.5 mL of whole venous blood for the determination of:

- CBC (WBC, Hb, platelets) with differential
- Glucose, Cr, AST, ALT, total bilirubin
- Viral serologies (HBsAg, anti-HCV Ab, and anti-HIV Ab)
- Collect urine from all females of childbearing potential for urine pregnancy test

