9.3. Methods/Timing for Assessing, Recording, and Analyzing Immunogenicity Endpoints

9.3.1. Pre-screening Prior to Enrollment

Subjects will be screened to ensure they are negative for hantavirus neutralizing antibodies prior to enrollment as defined by HTNV- or PUUV-specific titer <20 as measured by PsVNA50. Serum samples collected at the study site will be sent to USAMRIID. Serum samples will be stored at USAMRIID NCDD. USAMRIID Molecular Virology Branch personnel will receive frozen sera from USAMRIID NCDD. The labels on the serum aliquots will be verified to ensure they include the correct information for each sample. Samples will be thawed on wet ice and then heat-inactivated at 56°C (± 1°C) for 30 ± 1 minutes in a water bath. Samples will then be stored at 4°C (± 2°C) until assays are performed. The pre-screening assays will be performed approximately 2 weeks after arrival at USAMRIID. Puumala virus and Hantaan virus PsVNA will be performed in accordance with USAMRIID SOP AP-05-16 “Pseudovirion Neutralization Assay.” Screening results will be reported to CVD in a timely manner to assess subject inclusion/exclusion, but it has been communicated that the results can take up to 4 weeks to be made available. If pre-screening samples are positive for Puumala or Hantaan neutralizing antibodies as measured by PsVNA in 2 independent assays, then that subject would be excluded from the study.

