11.1. Description of Statistical Methods

Descriptive analysis of safety and reactogenicity outcomes will include all subjects who meet the eligibility criteria, receive at least one vaccination, and for whom safety data are available. Summary tables will be created in which incidence, severity, and relationship to the use of investigational product of individual solicited local and systemic signs, symptoms, or trending unsolicited events are delineated by study group, severity, gender, and overall. Unsolicited AEs and SAEs will be analyzed in a similar fashion.

Descriptive analysis of immunogenicity outcomes will include all subjects who meet the eligibility criteria, receive at least one vaccination, and for whom serological data are available. The primary analysis variable will be the proportion of seropositive subjects (defined as $\text{PsVNA50} \geq 1:20$) at each scheduled time point for which blood samples are taken (eg, Days 0, 28, 56, 84 and 140), and the final overall rate of seroconversion over all scheduled time points to study completion for each study group. Seroconversion is defined as a post-vaccination HTNV- or PUUV-specific titer of $\geq 1:40$, or a minimum four-fold rise compared to baseline titer and all study volunteers will begin the study with a baseline titer < 20 (ie, seronegative). For each study group, a binomial proportion and 95% confidence interval (CI) will be calculated. The secondary analysis variable will be geometric mean titers (GMT), with 95% CIs, of the PsVNA50 for HTNV- and PUUV-specific antibodies at each scheduled time point for which blood samples are taken for each study group and over all time points for each study group. GMT, standard errors, and 95% CIs will be calculated using log-transformed titers. For titers below the lower limit of detection (< 20), the value will be transformed to a value equal to the lower limit of detection (ie,

20) divided by the square root of 2, which equals 14.1. Exploratory objectives may evaluate PsVNA80 titers, which may be calculated for informational purposes, and may evaluate PsVNA50 titers against related Seoul and Dobrava viruses.

For hematology and serum chemistry tests, any clinically significant changes from baseline value will be identified. The median, interquartile range, and normal values for each laboratory value (as determined by the contract laboratory) will be reported for each treatment group for each specimen collection point.

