3.4. Secondary Endpoints

The secondary endpoints align with the immunogenicity objectives.

Secondary endpoints, correlating to the secondary objectives of the study will be to determine the proportion of seropositive subjects ($\text{PsVNA50} \geq 1:20$) and the final overall rate of seroconversion over all scheduled time points to study completion for each study group. GMT will be calculated using PsVNA50.

- Determination of the proportion of seropositive subjects (defined as $\text{PsVNA50} \geq 1:20$) at each scheduled time point (eg, Days 0, 28, 56, 84, 140, and 220)
- Determination of the final overall rate of seroconversion over all scheduled time points to study completion for each study group. Seroconversion is defined as a post-vaccination HTNV- or PUUV-specific titer of $\geq 1:40$, or a minimum four-fold rise compared to baseline titer, and all study volunteers will begin the study with a baseline titer < 20 (ie, seronegative).
- Determination of GMT of the PsVNA50 for HTNV- and PUUV-specific neutralizing antibodies at each scheduled time point for each study group and over all time points for each study group.

Exploratory endpoints:

Exploratory endpoints, evaluated as part of the immunogenicity objectives, including calculation of PsVNA80 titers for HTNV and PUUV may be calculated from the collected data for informational purposes, and neutralization assays using other hantavirus PsV (eg, Seoul virus, Dobrava virus) may also be performed to evaluate levels of cross-neutralizing antibodies.

- Determination of GMT of neutralizing of the PsVNA80 for HTNV- and PUUV-specific neutralizing antibodies at each scheduled time point for which blood samples are taken for each study group and over all time points for each study group
- Determination of GMT of neutralizing of the PsVNA50 and 80 for Seoul- and Dobrava-specific neutralizing antibodies at each scheduled time point for which blood samples are taken for each study group and over all time points for each study group

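### The four-fold limb of the seroconversion definition can never operate, so the rule is any post-dose titer of at least 1:40 and relies on a Day 0 titer below 20 that the plan asserts but does not use.

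*Protocol*

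**What the plan says.** **Definition.** Protocol Section 9.2.1 accepts either a titer of at least 1:40 "or a minimum four-fold rise compared to baseline titer, and all study volunteers will begin the study with a baseline titer < 20". The same two-limb rule stands in the Synopsis, Protocol Sections 6.1 and 11.1, and SAP Section 3.4 ("or a minimum four-fold rise compared to baseline titer"). None of them says whether baseline means the Screen 2 or the Day 0 sample.

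**Values below detection.** Protocol Section 11.1 replaces a titer below 20 by 20 "divided by the square root of 2, which equals 14.1"; SAP Section 9 does the same. Both state it for the geometric mean titers.

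**Entry.** Inclusion criterion 9 (Section 7.3) asks for a negative PsVNA result at screening. The sample is taken at Screen 2, whose window is Day -90 to Day -7; Section 8.1.1 adds "Potential subjects will undergo screening no more than 90 days prior to their planned initial injection". Section 8.1.2 turns away "Those who are seropositive, as defined by a Hantavirus PsVNA50 titer" of 20 or more. Section 9.3.1 excludes those "positive for Puumala or Hantaan neutralizing antibodies as measured by PsVNA in 2 independent assays". When more than 56 days pass, the safety laboratory tests are rechecked, but no repeat PsVNA is called for.

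**Day 0.** Section 9.3.2 has serum drawn on Day 0 for PsVNA, with all titers reported to the investigator only once the final titer is known. Day 0 is a listed time point for seropositivity and GMT. Section 9.1 requires a valid pre-vaccination result for the immunogenicity analysis but sets no condition on its value, and the SAP Section 6.3.2 population has no serostatus condition.

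**The concern.** A definition that names a four-fold rise suggests protection against counting pre-existing antibody as a vaccine response. Joined by an or to a fixed threshold, it gives none. The whole burden falls on the statement that everyone starts below 20. That statement is checked on a sample taken at least a week and possibly 90 days before dosing. The Day 0 result that would confirm it arrives too late to affect entry and has no assigned use.

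Seroconversion is one of the three measures (with seropositivity and GMT) by which Protocol Section 5.2 identifies the most immunogenic formulation and route, and SAP Table 4.3 compares it between pairs of groups. With about 10 to 12 subjects per group, one misclassified subject is visible in the rate. If a Day 0 positive does appear, someone must decide how to classify that subject with the data in view.

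**Working it through.** **1. The plan's own figure.** 20 / √2 = 14.14, which matches the stated 14.1.

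**2. When could the four-fold limb add anyone?** Only if 4 × baseline < 40, that is, baseline < 10. The lowest assigned value is 14.1, and 4 × 14.14 = 56.6 > 40. A check of 14.1 and every whole-number titer from 20 to 5000 finds no baseline with a four-fold value below 40. The documents give the 14.1 substitution for GMTs and no other value for fold rise. Even with an assumed substitute of 10, 4 × 10 = 40 and the limb still adds nobody.

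**3. What the written rule requires.** Titer needed = min(40, 4 × baseline), which is 40 throughout. Rise needed = 40 / Day 0 titer.

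| Day 0 titer | 4 × Day 0 | Titer needed as written | Rise needed as written | Titer needed if conditional on Day 0 |
|---|---|---|---|---|
| <20 (14.1) | 56.6 | 40 | 2.83-fold | 40 |
| 20 | 80 | 40 | 2.00-fold | 80 |
| 39 | 156 | 40 | 1.03-fold | 156 |
| 40 | 160 | 40 | none | 160 |
| 80 | 320 | 40 | none; a fall by half still counts | 320 |

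The two rules agree when Day 0 is below 20. Above that the written rule is always the easier one, so relative to the conditional rule any error can only raise a rate.

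**4. Size per subject.** 1/12 = 8.3 points; 1/10 = 10 points. If all 22 subjects planned for Group 6 are analysed, 1/22 = 4.5 points.

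**5. Against the plan's benchmark.** Protocol Section 11.2 asks for 7/10 to support a true rate of at least 30%. The exact two-sided 95% lower bound is 34.8% for 7/10 and 26.2% for 6/10, so 7 is reproduced as the smallest sufficient count. If one of the seven had an unchanged Day 0 titer of 40 or more, the result becomes 6/10 (26.2%), or 6/9 if that subject is removed (29.9%). Both fall below 30%. This depends on the interval: with a one-sided exact bound (30.4%) or a two-sided Wilson bound (31.3%), 6/10 would still pass.

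**6. How often?** The documents give no rate. As an assumption only, if 0%, 1% or 2% of subjects had Day 0 ≥40, the expected number among 82 is 0, 0.8 or 1.6. The chance of at least one in a group of 12, 1 − (1 − q)^12, is 0%, 11.4% or 21.5%.

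**The case against.** The strongest reply is that the clause on a baseline below 20 is part of the definition. Among subjects who satisfy it, 1:40 already means at least 2.83 times the assigned value, and the four-fold limb is harmless redundancy. That stands. But if the clause is a condition, a Day 0 positive is left unclassified, which is still a gap.

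It is also fair that such subjects should be rare. Section 7.4 excludes prior hantavirus infection, earlier HTNV, PUUV or Andes vaccine trials, planned endemic travel and recent blood products. Any case would show in the Day 0 tabulation. SAP Section 5 calls all analyses exploratory. These points limit the consequence; they do not supply the missing rule.

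Some stronger readings are tempting and are not supported:

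- *Any Day 0 positive converts with no rise.* This needs a Day 0 titer of 40 or more; at 20 to 39 some rise is still required.
- *Screening admits a subject positive for one virus.* Section 9.3.1 excludes a positive for either.
- *Needing two positive assays is a lax screen, as is the Section 9.2 rule that after a discordant re-titer "then the more conservative < 20 value will be used".* Section 9.1 defines a positive as at least 1:20 in two independent assays, for Screen 2 and later samples alike. A discordant pair is negative by the plan's own definition. Section 8.1.2 is worded more strictly, which is a matter of reconciling text.
- *The retest trigger for duplicates more than four-fold apart shows that a two-fold change is noise.* It is a quality check on one specimen, not a statement of error in a reported titer.
- *Ninety days is the usual gap.* It is the outer limit; the Synopsis describes up to 56 days of screening, although Section 8.1.2 expressly allows for a Screen 2 outside that window.

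**Conclusion.** The point holds as a minor defect of definition. As written, the four-fold limb is inert and seroconversion equals any post-dose titer of at least 1:40. That is correct for every subject whose Day 0 titer is below 20, and the plan asserts but does not verify that this is everyone. For a Day 0 titer of 40 or more the written rule can count a subject with no rise; for 20 to 39, with at most a two-fold rise. Under the other reading of the baseline clause, these subjects have no classification.

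A reader might infer that the reported rates will be inflated. The documents do not support that: they give no rate of Day 0 positivity, the entry criteria make it probably low, and if it is zero no result changes. The conclusion rests on the below-detection value being 10 or higher when fold rise is computed, and on Day 0 being the natural baseline.

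**What to change.** Before database lock, state in the Synopsis, Protocol Sections 6.1, 9.2.1 and 11.1, and SAP Section 3.4 that baseline is the Day 0 PsVNA50 titer for the same virus, and that seroconversion is:

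- a post-vaccination titer of at least 1:40 if the Day 0 titer is below 20;
- at least a four-fold rise over Day 0 if the Day 0 titer is 20 or more.

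This classifies every subject with a Day 0 result and needs no new sample or assay. Protocol Section 11 has the SAP finalized before lock, so the rule can still be prespecified. The cost is a sentence or two in each place. The downside is small: a noisy Day 0 reading of 20 would oblige a genuine responder to reach 1:80, although the re-titer rule in Section 9.2 would reset some such readings to below 20.

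Screening eligibility should stay as it is. Appendix B reports 36 subjects already enrolled by March 2020, and tightening entry now would give earlier and later groups different criteria. At most, align the wording of Protocol Sections 8.1.2, 9.1 and 9.3.1 on what counts as a positive screen.
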